2.6 Analysis supporting secondary objectives

The secondary objectives in this study are as follows:

- To evaluate the safety and tolerability of asciminib in subjects with CML-CP following two or more prior TKI treatments for SAF and SAF 2.
- To assess the rate of MMR in subjects with no evidence of MMR at baseline, at alternative time points at weeks 12, 24, 36, 72, 96 and 144 for FAS.
- To assess the rate of MMR at week 48 for subjects with MMR at baseline for FAS 2.
- To assess the time to MMR for FAS.
- To assess the rate of early responses of BCR::ABL1 $\leq 10\%$ and $\leq 1\%$ IS at weeks 12, 24, 36 and 48 for FAS.
- To assess the rate of deep molecular responses (MR4 and MR4.5) at weeks 12, 24, 36, 48, 72, 96 and 144 for FAS.
- To assess cytogenetic response (% Ph+ metaphases) at weeks 48 and EOT for FAS.
- To characterize the impact of additional cytogenetic abnormalities on efficacy for FAS.
- To assess cumulative molecular responses by all-time points for FAS.
- To assess duration of MMR for FAS and FAS 2.
- To assess sustained deep molecular responses as prerequisite for TFR for FAS and FAS 2.

- To assess rate of progression (PFS) for FAS.
- To assess overall survival (OS) for FAS.
- To assess time to treatment failure (TTF) for FAS.
- To evaluate patient reported outcomes and quality of life by using QoL scales for FAS and FAS 2.

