1st and 2nd treatment, the 2020 ELN recommendations represent only one set of criteria that is consistent for 1st line and 2nd line treatment. In general, these 2020 treatment milestones define a more ambitious set of response criteria over their 2013 counterpart: in the 2013 ELN recommendations, treatment failure in second-line was defined as: no CHR at 3 months, BCR-ABL1>10% on the International Scale (IS) at 6 months or 12 months. For the 2020 recommendations the milestones for treatment failure have been revised to BCR-ABL1>10% IS at 3 months (if confirmed between 1 and 3 months) and at 6 months, or BCR-ABL1>1% IS at 12 months of therapy. Warning criteria in 2nd line are identified as: BCR-ABL1>10% IS at 3 months, BCR-ABL1>1-10% IS at 6 months and BCR-ABL1>0.1-1% IS at 12 months. As these recommendations represent the profound change of the therapeutic landscape over the last 7 years ([Hochhaus et al 2020a](#)) it is considered important to re-evaluate the benefit of asciminib in a 3rd line population if the most recent treatment recommendations for failure and warning in 2nd line are used as inclusion criteria.

The ASCSEMBL study investigated the efficacy and safety of a total daily dose of 80 mg asciminib given as one tablet of 40 mg b.i.d. Asciminib is required to be administered under fasting conditions with a food-free period of 2 hour before and 1 hour after the drug intake [Asciminib Investigator Brochure]. Non adherence to TKI therapy in CML has been correlated with poor therapeutic outcomes and is a principal factor contributing to the loss of cytogenetic responses and treatment failures in patients on long-term therapy ([Ibrahim et al 2011](#)) In a Finnish assessment, 21% of the CML patients were characterized to have low adherence, while physicians had a tendency to overestimate adherence ([Keläle et al 2014](#)). Nilotinib has a similar posology to that of asciminib as used in the ASCSEMBL study, with twice daily dosing and the inclusion of a food-free period. In an analysis of 2546 patients in 63 countries. ([Geissler et al 2017](#)) showed that the adherence to nilotinib was markedly lower than for imatinib and dasatinib, both of which can be taken on a once daily regimen.

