1.2 Purpose

The purpose of the study is to investigate the potential optimization of the treatment with asciminib 80 mg total daily dose in adult patients with chronic myelogenous leukemia in chronic phase (CML-CP) previously treated with 2 or more TKIs.

Patient population:

Patients for this study will be identified based on warning criteria and resistance definition following ELN 2020 recommendations or intolerance on their 2nd TKI ([Hochhaus et al 2020a](#)). This is an expanded population compared to the original ASCSEMBL study as the inclusion criteria for the ASCSEMBL-protocol was based on the ELN treatment recommendations from 2013 ([Hochhaus et al 2020c](#)). Applying the newer ELN 2020 criteria will permit patients both with treatment failure as well as with warning signs to be included. This will allow for a population, with less advanced disease and lower risk of progression to enter the trial, which may benefit from a better and longer response to asciminib.

Patients treated with two or more TKI and intolerance to the last TKI treatment represent a clinical challenge as the number of treatment options available to them are limited. For the primary analysis, patients with intolerance will be eligible with BCR-ABL1 $\geq 0.1\%$ (i.e. not in MMR). Additionally, 30 patients who are intolerant to ongoing TKI treatment but in MMR will be allowed to enter the trial.

Simplified posology from b.i.d. to q.d. dosing:

The study will investigate the use of two different dose regimens: All patients will be randomized at baseline to receive 80 mg total daily dose of asciminib either as 40 mg b.i.d. in agreement with the dose investigated in ASCSEMBL or as 80 mg q.d. Though the trial will not be powered to compare both treatments, the descriptive data from both treatment groups is expected to provide additional insight into the optimal patient management.

Dose escalation:

Patients treated in later lines of CML often have few remaining therapeutic options. Asciminib has demonstrated activity and tolerability in dosages of up to 200 mg b.i.d. ([Hughes et al 2019](#)). With the limited treatment options available it is therefore of interest whether patients not in MMR at 48 weeks or thereafter could benefit from a potential dose escalation. Based on extensive PK modeling, a dose escalation from 40 mg b.i.d. / 80 mg q.d. asciminib to 200 mg q.d. asciminib was chosen for this approach.

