5.1 Inclusion criteria

Participants eligible for inclusion in this study must meet **all** the following criteria:

1. Signed informed consent must be obtained prior to participation in the study
2. Male or female patients with a diagnosis of CML-CP \geq 18 years of age
3. Patients must meet all the following laboratory values at the screening visit:
 - $< 15\%$ blasts in peripheral blood and bone marrow
 - $< 30\%$ blasts plus promyelocytes in peripheral blood and bone marrow
 - $< 20\%$ basophils in the peripheral blood
 - $\geq 50 \times 10^9/L$ ($\geq 50,000/mm^3$) platelets
 - Transient prior therapy related thrombocytopenia ($< 50,000/mm^3$ for ≤ 30 days prior to screening) is acceptable
 - No evidence of extramedullary leukemic involvement, with the exception of hepatosplenomegaly
4. Prior treatment with a minimum of 2 prior TKIs (i.e. imatinib, nilotinib, dasatinib, bosutinib, radotinib or ponatinib)
5. Warning or failure (adapted from the 2020 ELN Recommendations) or intolerance to the most recent TKI therapy at the time of screening
 - Warning is defined as:
 - Three months after the initiation of treatment: BCR-ABL1 $> 10\%$ IS
 - Six months after the initiation of treatment: BCR-ABL1 $> 1-10\%$ IS
 - Twelve months after the initiation of treatment BCR-ABL1 $> 0,1-1\%$ IS

- At any time after the initiation of therapy BCR-ABL1 >0.1-1% IS, loss of MMR (>0.1% with 5-fold increase of BCR-ABL1 transcripts).
 - In addition, patients with failure of treatment according to the ELN 2020 recommendations will be eligible:
 - Three months after the initiation of treatment: BCR-ABL1 > 10% IS if confirmed within 1-3 months
 - Six months after the initiation of treatment: BCR-ABL1 >10% IS
 - Twelve months after the initiation of treatment BCR-ABL1 >1% IS
 - At any time after the initiation of therapy BCR-ABL1 >1% IS, emergence of resistance mutations, high-risk ACA
 - Intolerance is defined as:
 - Non-hematologic intolerance: Patients with grade 3 or 4 toxicity while on therapy, or with persistent grade 2 toxicity, unresponsive to optimal management, including dose adjustments (unless dose reduction is not considered in the best interest of the patient if response is already suboptimal)
 - Hematologic intolerance: Patients with grade 3 or 4 toxicity (absolute neutrophil count [ANC] or platelets) while on therapy that is recurrent after dose reduction to the lowest doses recommended by manufacturer

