2.2 Analysis sets

The subject population for the study includes subjects resistant or intolerant to 2 or more prior TKI treatments without MMR at baseline, and an additional group of subjects who were intolerant to the last TKI and were in MMR at baseline. Note that the YR data domain from IRT will be used to identify the stratification groups for the study population, and the biomarker data (B1 domain) containing BCR::ABL ratio will be used to confirm the MMR status at baseline for all subjects. If there is discrepancy between YR and B1 data, the MMR status at baseline will be assessed based on the B1 data.

The Analysis Sets are stated as follows:

Full Analysis Set

The Full Analysis Set (FAS) comprises all participants to whom study treatment has been assigned by randomization except the additional subjects who were intolerant to the last TKI and were in MMR at baseline.

Full Analysis Set 2

The Full Analysis Set 2 (FAS 2) comprises only the additional subjects who were intolerant to the last TKI and were in MMR at baseline and to whom study treatment has been assigned by randomization.

Safety Set

The Safety Set (SAF) includes all participants who received at least one dose of study treatment except the additional subjects who were intolerant to the last TKI and were in MMR at baseline.

Safety Set 2

The Safety Set 2 (SAF 2) includes only the additional subjects who were intolerant to the last TKI and achieved were in MMR at baseline and who received at least one dose of study treatment.

Unless otherwise stated, the analysis sets will be applied as below:

- For the subjects resistant or intolerant to 2 or more prior TKI treatments without MMR at inclusion to the trial
 - The FAS will be used for demographics and baseline characteristics (except disease characteristics) and all efficacy analyses including PROs
 - The SAF will be used for baseline disease characteristics, exposure and all safety analyses
- For the additional subjects who were intolerant to the last TKI and were in MMR at baseline
 - The FAS 2 will be used for demographics and baseline characteristics (except disease characteristics) and selected efficacy analyses including PROs
 - The SAF 2 will be used for baseline disease characteristics, exposure and selected safety analyses

Withdrawal of Informed Consent

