2.6.1.2 Cytogenetic response

At each assessment time point the cytogenetic response status of each subject is classified as complete, partial, major, minor, minimal response and none (a review of a minimum of 20 metaphases is required):

- Complete response (CCyR): 0% Philadelphia chromosome positive (Ph+) metaphases
- Partial response (PCyR): >0 to 35% Ph+ metaphases

- Major response (MCyR = CCyR + PCyR): 0 to 35% Ph+ metaphases
- Minor response (mCyR): >35 to 65% Ph+ metaphases
- Minimal response: >65 to 95% Ph+ metaphases
- None: >95 to 100% Ph+ metaphases.

Bone marrow aspirate for cytogenetic analyses will be performed at screening/baseline (performed up to 56 days prior to Week 1 Day 1), at Week 48 and at EOT (only required if the subject discontinues from the study early due to lack/loss of response). In case no bone marrow aspirate was performed but the subject is in MMR at a specific time-point, the subject is considered to have achieved CCyR at that time-point. The date of CCyR is imputed by the date of MMR at the same scheduled time-point.

CCyR rates at Week 48 and EOT. Such rates are defined as the proportion of subjects in CCyR at the respective time points, which excludes subjects who are in CCyR at baseline.

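### The 'early response' rates (BCR::ABL1 ≤10% and ≤1%) use the whole FAS, which can include patients already at those levels at entry, so they mix maintenance with new response

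*SAP*

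**What the plan says.** **Endpoint and analysis set.** SAP 2.6 lists the objective "To assess the rate of early responses of BCR::ABL1" ≤10% and ≤1% "at weeks 12, 24, 36 and 48 for FAS". SAP 2.6.2 adds the cumulative rates for the same two thresholds. Protocol 12.5.1 also uses the FAS.

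**Who is in the FAS.** Under SAP 2.2 it "comprises all participants to whom study treatment has been assigned by randomization except the additional subjects" who were intolerant to their last TKI and in MMR at baseline. No other baseline level removes a patient.

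**Who may enter.** Protocol 1.1 gives ELN 2020 warning levels that include "BCR-ABL1>1-10% IS at 6 months and BCR-ABL1>0.1-1% IS at 12 months". Protocol 5.1 has the further warning criterion "At any time after the initiation of therapy BCR-ABL1 >0.1-1% IS, loss of MMR", and admits failure at >1% from 12 months or at any time. On intolerance, Protocol 1.2 states: "For the primary analysis, patients with intolerance will be eligible with BCR-ABL1" of 0.1% or more. The same section says of the wider criteria: "This will allow for a population, with less advanced disease and lower risk of progression to enter the trial".

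**Scoring.** For at-visit rates, SAP 2.6.2 makes a patient a non-responder after treatment discontinuation or when no assessment is available. Nothing refers to the baseline level.

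**Contrast.** SAP 2.6.1.2 defines the CCyR rate as one "which excludes subjects who are in CCyR at baseline". Baseline shift tables are specified in SAP 2.6.2 for cytogenetic response only.

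**The concern.** A response rate is normally read as the share of patients whom treatment brought to a given level. Here part of the denominator may be at that level before the first dose. For those patients the event being counted is staying at or below the level, and a value that rises within the band still scores as a response.

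The reported rate therefore depends on case mix at entry as well as on what asciminib achieves. Two cohorts with the same new-response rate would report different early-response rates if one enrolled more patients at lower levels, and this protocol deliberately widens entry in that direction. Protocol 8.3.2 gives comparison with other data as one reason for reporting on the International Scale, so readers are likely to set these rates beside others without seeing the entry mix.

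**Working it through.** **1. The plan's own figure.** The documents state no expected value for the early-response rates. The one design figure is 80% power for Week 48 MMR (n = 156, null 23%, alternative 33%, one-sided 0.025). The exact binomial test rejects from 47/156, with attained alpha 0.0241 and power 0.801. The lower 95% Clopper-Pearson bound at 47/156 is 23.05%. The figure reproduces and is not in question here.

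**2. Entry levels against the two thresholds** (Protocol 1.1, 1.2 and 5.1).

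| Route into the FAS | Qualifying level | Already ≤10%? | Already ≤1%? |
|---|---|---|---|
| Warning, 3 months | >10% | No | No |
| Warning, 6 months | >1–10% | Yes | No |
| Warning, 12 months or any time | >0.1–1% | Yes | Yes |
| Failure, 3 or 6 months | >10% | No | No |
| Failure, 12 months or any time | >1% | Yes, if up to 10% | No |
| Intolerance, not in MMR | ≥0.1% | Possible | Possible |

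So the ≤10% rate is affected through warning, failure and intolerance, and the ≤1% rate through warning and intolerance.

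**3. One patient followed through the rules.** Suppose baseline is 0.5%, Week 12 is 0.6%, and treatment continues. The patient is a Week 12 responder for both thresholds although the value rose. SAP 2.6.1.1 spells out, for MMR, that a response once reached counts at later time points even if lost. Read across to ≤10% and ≤1%, that single value makes the patient a cumulative responder at every later visit. SAP 2.1.1 opens the Week 12 window on Day 2 and says efficacy summaries include data from baseline. It does not say whether the baseline value itself can count.

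**4. Size.** Let b be the share of the FAS already at the threshold, m the share of those still on treatment and at the level at the visit, and q the response rate among patients above the threshold at baseline. Then

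reported rate R = b·m + (1 − b)·q, so R − q = b·(m − q).

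None of b, m or q is in the documents. The values below are assumptions that show the range, with q = 0.30.

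| b | R at m = 1 | R at m = 0.9 | Share of R from patients already there (m = 1) |
|---|---|---|---|
| 0 | 0.30 | 0.30 | 0% |
| 0.20 | 0.20 + 0.24 = 0.44 | 0.18 + 0.24 = 0.42 | 0.20/0.44 = 45% |
| 0.40 | 0.40 + 0.18 = 0.58 | 0.36 + 0.18 = 0.54 | 0.40/0.58 = 69% |
| 0.60 | 0.60 + 0.12 = 0.72 | 0.54 + 0.12 = 0.66 | 0.60/0.72 = 83% |

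At m = 1, each 10 percentage points of b adds 0.10 × (1 − 0.30) = 0.07. At m = 0.9 it adds 0.10 × (0.90 − 0.30) = 0.06. In the limit q = 0 and m = 1, R equals b: a 20–60% rate with no new response at all.

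**5. Precision of a restricted rate.** Clopper-Pearson 95% intervals at about 30%:

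- b = 0: 47/156, 23–38%
- b = 0.20: 156 × 0.80 ≈ 125; 38/125, 22–39%
- b = 0.40: 156 × 0.60 ≈ 94; 28/94, 21–40%
- b = 0.60: 156 × 0.40 ≈ 62; 19/62, 20–44%

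For ≤10% the share already there could be higher. At an assumed 90%, 156 × 0.10 ≈ 16 patients remain, and 6/16 gives 15–65%.

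**The case against.** The strongest defence is that the all-FAS proportion is a legitimate quantity. The endpoint is a rate of being at or below a level at fixed visits, and the protocol is built on absolute ELN milestones. Protocol 9.1.1 treats >1% at 48 weeks as treatment failure, so the share of all patients at ≤1% at that visit is informative in itself. The plan also counts maintenance deliberately elsewhere: Week 48 MMR in patients already in MMR is a separate endpoint on FAS 2. And no secondary endpoint is tested. All of this stands. It is why the all-FAS rate should be kept, and why the complaint is about its label and the missing companion rate.

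Three stronger readings are tempting and are not supported:

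- **That these patients count without any treatment effect.** For at-visit rates they must still be on asciminib, assessed and at the level, after stopping a TKI that was failing or not tolerated. Holding the level is disease control on study drug. What is true is that no improvement is required.
- **That the rate mainly reflects how mild the population was.** This rests wholly on assumed baseline shares. At b = 0.20 in the table, new responders are the majority (0.24 of 0.44).
- **That the SAP handles this for every other response endpoint.** Only CCyR has an explicit exclusion within the FAS. Patients in MMR are outside the FAS because they form a separate cohort.

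A partial mitigation is that SAP 2.6.2 tabulates all molecular categories at each time point, and Table 2-1 has a baseline row. If baseline is tabulated, readers will see entry levels. The SAP does not say that it will be, and marginal counts cannot separate patients who moved from patients who stayed.

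**Conclusion.** The gap is in the text: whole-FAS rates, entry criteria that admit patients already at the thresholds, scoring rules that ignore baseline level, and a baseline exclusion and shift table for cytogenetic response only. As labelled, the early-response rate cannot be read as a rate of new response to asciminib. Warning patients who enter at >10% are unaffected.

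The size is unknown. Per 10 points of the FAS already at the threshold, the excess over q is 7 points at q = 30% with full retention, and 6 points with 90% retention. Both conversion and retention are assumed.

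The consequence is limited to interpreting descriptive secondary rates. The documents plan no external comparison on these endpoints. The external benchmark concerns Week 48 MMR, and the primary test, alpha and sample size are untouched. This is a cheap improvement, not a flaw in the trial's main conclusion.

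**What to change.** In SAP 2.6.1.1 and 2.6.2:

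1. Keep the all-FAS rates, labelled as the proportion at or below the threshold (including at baseline).
2. Add, for both the at-visit and the cumulative rates, the rate with its Clopper-Pearson interval among FAS subjects above that threshold at baseline: >10% for the ≤10% rate and >1% for the ≤1% rate. Call this the early-response rate, and state that only post-baseline values count.
3. Add a shift table of molecular response category, baseline by visit.
4. Record the addition in SAP Section 4, which now reads as not applicable.

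No new data are needed, since Protocol 8.1 requires the central RQ-PCR result before enrolment. The work is a few sentences, a baseline filter and one table. The price is a smaller denominator, possibly very small for ≤10%, wider intervals and a less favourable figure. Keeping the all-FAS row means Protocol 12.5.1 is still reported as written.

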2.6.1 Secondary endpoint(s)

No statistical testing of secondary efficacy endpoints will be performed.

2.6.1.1 Molecular response

MMR rates at all scheduled data collection time points, i.e., the protocol-planned visits except for 48 weeks which is already covered by primary endpoint. Such rates are defined as the proportion of subjects with MMR at the respective time points.

MMR rates by all scheduled data collection time points, i.e., the protocol-planned visits. These are cumulative MMR rates by time points and are defined as the proportion of subjects who achieve MMR at or before specified visits, i.e. if a subject achieves an MMR but then loses it before or at a specific visit, he/she will still be classed as achieving MMR by that specific time point. Subjects without any documented response for which an evaluable response assessment was never provided will be considered as non-responders for the period of time up to that time point.

Molecular response category at specific time points, i.e., the protocol-planned visits. Categories of molecular response are defined in Appendix.

Molecular response category by specific time points, i.e., the protocol-planned visits. This is defined as the molecular response category up to the specific time points.

Time to MMR (in weeks) is defined as: $(\text{date of first documented MMR} - \text{date of randomization} + 1)/7$.

Duration of MMR is defined in protocol section 8.3.1.1 as the time from the date of first documented MMR to the earliest date of confirmed loss of MMR, progression to accelerated phase (AP) or blast crisis (BC), or CML-related death. Loss of MMR and progression to accelerated phase (AP)/blast crisis (BC) are defined in Appendix.

The duration of MMR (in weeks) is calculated as: $(\text{end date or censoring date of MMR} - \text{date of first MMR} + 1)/7$.

2.6.1.2 Cytogenetic response

At each assessment time point the cytogenetic response status of each subject is classified as complete, partial, major, minor, minimal response and none (a review of a minimum of 20 metaphases is required):

- Complete response (CCyR): 0% Philadelphia chromosome positive (Ph+) metaphases
- Partial response (PCyR): >0 to 35% Ph+ metaphases

- Major response (MCyR = CCyR + PCyR): 0 to 35% Ph+ metaphases
- Minor response (mCyR): >35 to 65% Ph+ metaphases
- Minimal response: >65 to 95% Ph+ metaphases
- None: >95 to 100% Ph+ metaphases.

Bone marrow aspirate for cytogenetic analyses will be performed at screening/baseline (performed up to 56 days prior to Week 1 Day 1), at Week 48 and at EOT (only required if the subject discontinues from the study early due to lack/loss of response). In case no bone marrow aspirate was performed but the subject is in MMR at a specific time-point, the subject is considered to have achieved CCyR at that time-point. The date of CCyR is imputed by the date of MMR at the same scheduled time-point.

CCyR rates at Week 48 and EOT. Such rates are defined as the proportion of subjects in CCyR at the respective time points, which excludes subjects who are in CCyR at baseline.

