8.3.1.2 Bone marrow analysis and cytogenetics

Cytogenetic response will be assessed as the percentage of Ph+ metaphases in the bone marrow and is defined as the following (a review of a minimum of 20 metaphases is required):

- Major (MCyR) - 0 to 35% Ph+ metaphases
- Complete (CCyR) - 0% Ph+ metaphases
- Partial (PCyR) - >0 to 35% Ph+ metaphases
- Minor (mCyR) - >35 to 65% Ph+ metaphases
- Minimal - >65 to 95% Ph+ metaphases
- None - >95 to 100% Ph+ metaphases.

Bone marrow aspirate for cytogenetic analyses will be performed at screening/baseline (performed up to 56 days prior to Week 1 Day 1), at Week 48 and at EOT (only required if the patient discontinues from the study early due to lack/loss of response). Should bone marrow assessments have been performed before the main informed consent is signed but within 56 days of Week 1 Day 1, no further bone marrow sampling will be required at screening and local assessment data will be collected.

Quantification of the percentage of Ph+ chromosome metaphases, number of metaphases, number positive for Ph chromosome, additional chromosomal abnormalities as well as data from cytologic evaluation (microscopic analysis) of percentage of blasts and promyelocytes

will be recorded on the Bone Marrow eCRF. These exams will be performed and analyzed locally.

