If more than one assessment is assigned to the same time window, the assessment performed closest to the target date will be used for by-visit statistical analyses. If 2 assessments within a visit window are equidistant from the target date, then the average of the 2 assessments will be used. If multiple assessments are on the same date, then the the average will be used. Data from all assessments (scheduled and unscheduled), including multiple assessments, will be listed.

Table 2-1 Time windows for molecular response

Assessment	Target day of assessment	Time Interval
Baseline	≤ 1	\leq Day 1 [#]
Week 12	85	Day 2 to day 127
Week 24	169	Day 128 to day 211
Week 36	253	Day 212 to day 295
Week 48	337	Day 296 to day 379
Week k (k=60, 72, ...)	$K \times 7 + 1$	Day $k \times 7 - 40$ – $k \times 7 + 43$

Day 1 = Date of randomization
EOT assessments are mapped to the time points as needed.

Table 2-2 Time windows for cytogenetic response

Assessment	Target day of assessment	Time Interval
Baseline	1	≤ Day 1 [#]
Week 48	337	Day 253 to day 420
EOT [*]	EOT	EOT

[#] Day 1 = Date of randomization. Should bone marrow assessments have been performed before the main informed consent is signed but within 56 days of Week 1 Day 1, no further bone marrow sampling will be required at screening and local assessment data will be collected.

^{*} Only required for Early Discontinuation due to lack of response / loss of response

For PRO data time windows will be defined for descriptive summary by visit. If more than one assessment is available in the same time window, the assessment closest to the planned date will be considered. If two assessments are obtained with the same time difference compared to the scheduled visit day, the assessment obtained prior to visit will be considered.

Table 2-3 Time windows for PRO: MDASI-CML

Assessment	Target day of assessment	Time Interval
Baseline	1	≤ Day 1 [#]
Week 4	29	Day 2 to day 57
Week 12	85	Day 58 to day 127
Week 24	169	Day 128 to day 253
Week 48	337	Day 254 to day 421
Week 72	505	Day 422 to day 589
Week 96	673	Day 590 to day 757
Week 120	841	Day 758 to day 925
EOT (Week 144)	1009	Day 926 to day 1009

[#] Day 1 = Date of randomization

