Subjects in FAS will be categorized with counts and percentages provided for cytogenetic response at week 48 and EOT. Shift tables will also be employed to examine the changes in cytogenetic response category from baseline.

CCyR rates at Weeks 48 and EOT and the associated 95% confidence intervals based on the Clopper-Pearson method will be presented.

TTF, PFS and OS

For each endpoint the survival distribution will be estimated using the Kaplan-Meier method, and Kaplan-Meier curves, medians and 95% confidence intervals [[Brookmeyer and Crowley](#)

[1982](#)] of the medians, along with the proportion of subjects who have not experienced the respective events at 1, 2 and 3 years and the associated 95% confidence intervals, will be presented.

TTF: For subjects in the FAS who have not reached treatment failure, their TTFs will be censored at the time of their last study assessment (PCR, cytogenetic, hematologic or extramedullary) before the cut-off date.

PFS: For subjects who have not experienced an event (disease progression to AP/BC or death from any cause), their PFS times will be censored at the date of last study assessment (PCR, cytogenetic, hematologic or extramedullary) before the cut-off date.

OS: Subjects who are alive at the time of the analysis data cutoff date will be censored at the date of last contact (see [Section 2.1.1](#)) before the cut-off date.

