5.4.2 Cytogenetic response

Cytogenetic response will be based on the percentage of Ph+ metaphases in the bone marrow. Cytogenetic evaluations will be considered for response assessment only if the number of metaphases examined is ≥ 20 in each bone marrow sample.

Cytogenetic response is categorized as follows (a review of a minimum of 20 metaphases is required):

- Complete response (CCyR): 0% Philadelphia chromosome positive (Ph+) metaphases
- Partial response (PCyR): >0 to 35% Ph+ metaphases
- Major response (MCyR = CCyR + PCyR): 0 to 35% Ph+ metaphases
- Minor response (mCyR): >35 to 65% Ph+ metaphases
- Minimal response: >65 to 95% Ph+ metaphases
- None: >95 to 100% Ph+ metaphases.

If bone marrow aspirate blast percentage is provided as ' $<X$ ' (i.e. below limit of detection), the numeric value is set to X for summary tables. In the listing ' $<X$ ' will be presented.

Complete cytogenetic response (CCyR)

CCyR is defined as a value of 0% Ph+ metaphases in bone marrow.

CCyR will be considered as a binary variable with subjects achieving CCyR grouped as 'responders' and subjects not achieving CCyR, subjects with missing cytogenetic evaluations grouped as 'non-responders'. In case no bone marrow aspirate was performed but the subject is in MMR at a specific time-point, the subject is considered to have achieved CCyR at that time-point. The date of CCyR is imputed by the date of MMR at the same scheduled time-point.

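### The CCyR rate planned at EOT undercounts subjects in CCyR without MMR: most need no marrow there, and without one they are scored as non-responders

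*SAP*

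**What the plan says.** SAP 2.6.2 states: "CCyR rates at Weeks 48 and EOT and the associated 95% confidence intervals based on the Clopper-Pearson method will be presented". Protocol 12.5.1 plans the same, and protocol Table 2-1 lists the EOT rate among the secondary endpoints. On the analysis set, SAP 2.6.2 adds: "Subjects in FAS will be categorized with counts and percentages provided for cytogenetic response at week 48 and EOT". SAP 2.6.1.2 narrows the rate to one "which excludes subjects who are in CCyR at baseline", without saying whether those subjects leave the numerator or the denominator.

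The marrow rule at EOT is the same in three places: SAP 2.6.1.2 ("only required if the subject discontinues from the study early due to lack/loss of response"), the footnote to SAP Table 2-2 ("Only required for Early Discontinuation due to lack of response / loss of response") and protocol 8.3.1.2 ("only required if the patient discontinues from the study early due to lack/loss of response"). At Week 48 marrow is scheduled for all subjects.

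SAP 5.4.2 treats CCyR as a binary variable, with "subjects with missing cytogenetic evaluations grouped as" non-responders. SAP 2.6.1.2 and 5.4.2 make one exception: a subject with no aspirate who is in MMR at the time point is taken to be in CCyR. PCR is scheduled at EOT (protocol Table 8-2), so this exception can operate there.

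**The concern.** Outside the group stopping early for lack or loss of response, no EOT marrow is required. For a subject without one, the EOT result is simply MMR status under the name of CCyR. Someone with no Ph+ metaphases and BCR-ABL1 above 0.1% is recorded as not in CCyR without having been examined.

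This group is probably not empty. Under protocol 9.1.1, failure at Week 48 means BCR-ABL1 above 1% or no CCyR, so a subject in CCyR at >0.1–1% does not fail on that criterion and may stay on treatment. Protocol 6.6.2 also expects some subjects not in MMR at Week 48 to continue.

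At stake is a reported secondary rate and CI that do not estimate what they name, and the reading of Week 48 against EOT. A subject in CCyR and steady between 0.1% and 1% is a responder at Week 48, where marrow is taken, and a non-responder at EOT, where it is not. The rate can fall with no change in disease.

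**Working it through.** **The plan's own figures.** The documents give no expected CCyR rate or precision, so there is nothing to reproduce for this endpoint. Their one power statement concerns MMR at Week 48 (156 subjects, 23% against 33%, one-sided 0.025, 80%). It reproduces: 47 responders are needed, exact alpha is 0.0241 and power is 0.801. The present point does not touch it.

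**Inputs.** N = 156 (SAP Section 3), used only as an illustrative base. Three proportions are not in the documents and are assumed:
- m, in MMR at EOT: 23%, 33% or 45%
- c, in CCyR but not in MMR at EOT: 0–20%
- s, the share of c with an EOT marrow that enters the rate: 0–50%

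**How the rules classify subjects at EOT**

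| True state | Marrow | Scored as |
|---|---|---|
| In MMR (taken as CCyR) | none | CCyR |
| CCyR, not MMR | yes | CCyR |
| CCyR, not MMR | none | not CCyR |
| Not CCyR, not MMR | yes or none | not CCyR |

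Only the third row is wrong. Hence:
- true rate = m + c
- planned rate = m + c × s
- bias = (m + c × s) − (m + c) = −c × (1 − s), which does not depend on m.

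**Results with m = 33%**

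| c | True rate | Planned, s = 0 | Bias, s = 0 | Bias, s = 50% |
|---|---|---|---|---|
| 0% | 33% | 33% | 0 | 0 |
| 5% | 38% | 33% | −5 points | −2.5 points |
| 10% | 43% | 33% | −10 points | −5 points |
| 20% | 53% | 33% | −20 points | −10 points |

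**Against the planned CI.** With s = 0, 0.33 × 156 = 51.5, taken as 51. The Clopper-Pearson interval for 51/156 is 25.4% to 40.7%. It covers the true rate at c = 5% (38%) but not at c = 10% (43%). The pattern is the same at m = 23% (16.7% to 30.5%, against true rates of 28% and 33%) and at m = 45% (36.9% to 53.0%, against 50% and 55%).

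**Baseline exclusion.** If subjects in CCyR at baseline leave the denominator, c applies to those who remain. With 100 remaining (assumed) and a planned rate of 33%, the interval is 23.9% to 43.1%. It covers 43% but not 53%. If they leave only the numerator, they count as non-CCyR whatever a marrow shows. Entry criteria admit subjects at >0.1–1%, so some may be in CCyR at entry, but the documents give no number.

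**The case against.** Five points can be made for the plan.

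1. The MMR exception limits the damage. A reader who saw only the missing-data rule might infer that every subject without a marrow is a failure. At m = 33% and s = 0 the planned rate would then be 0%, a bias of 33 to 53 points for c = 0–20%. The documents do not support that, because subjects in MMR without an aspirate count as CCyR. This stands, and the working uses the narrower form.
2. Missing data are visible. SAP 5.5.1 reports a separate missing category for cytogenetic response, split by treatment status and reason for stopping. It would therefore go too far to infer that the category summaries hide unassessed subjects. But the binary rule in 5.4.2 still governs the rate and CI.
3. Not requiring a marrow does not forbid one. That is right, and is why s is allowed to exceed zero.
4. A headcount is tempting. With 50–60% completing and 15–35% of completers ending at >0.1–1%, 156 × 0.50 × 0.15 ≈ 12 and 156 × 0.60 × 0.35 ≈ 33 subjects. The documents support neither input. The count also assumes that all of these subjects are in CCyR, have no marrow and were not in CCyR at baseline. In addition, confirmed loss of MMR is treatment failure (SAP 5.4.4), and later efficacy data are dropped (SAP 2.1.1), so some of these subjects would not enter at all. Adding the 5.1% who stopped for adverse events on asciminib in ASCEMBL (156 × 0.051 ≈ 8) fails likewise: those in MMR are rescued, and others may not be in CCyR.
5. The endpoint is descriptive. No secondary efficacy endpoint is tested, and the analysis by additional chromosomal abnormalities uses CCyR at Week 48 only. This limits the consequence but does not make the estimate right.

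**Conclusion.** The concern holds in a limited form. The EOT rate mixes marrow results, required only in subjects selected for poor response, with MMR status in the rest. It undercounts CCyR without MMR by c × (1 − s): 0 to 20 points for c = 0–20% with no marrows in that group, and 0 to 10 points if half have one. These ranges are assumptions, and the formula also takes MMR to imply CCyR, as the SAP does. The number of subjects affected cannot be stated, because the baseline exclusion is ambiguous and the documents give no data on c or s. The EOT rate should not be set against the Week 48 rate as if both were measured alike. The primary analysis and its conclusion are unaffected.

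**What to change.** Keep Week 48 as the time point for the CCyR rate and CI. At EOT, replace the single rate and CI with counts over all subjects in the analysis, by source: CCyR by marrow, CCyR imputed from MMR, not CCyR by marrow, and not assessed. If a rate is kept, give a lower bound with the not-assessed subjects as non-CCyR and an upper bound with them as CCyR.

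Do not restrict the denominator to subjects with a marrow or MMR, because response would then be a route into it. For illustration, assume 51 subjects in MMR and 20 with a marrow showing no CCyR. The restricted rate is 51/(51 + 20) = 72%, against 51/156 = 33% as planned. Bounds on the same figures, with 156 − 51 − 20 = 85 not assessed, run from 33% to (51 + 85)/156 = 87%. That width shows how little the EOT data say about CCyR.

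State whether subjects in CCyR at baseline leave the numerator or the denominator. Record the change in SAP Section 4, which now lists none.

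The cost is that one descriptive, protocol-listed rate is replaced by counts or bounds. No marrow is added.
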